5 Health-related biomedical or behavioral outcome is defined as the pre-specified goal(s) or condition(s) that reflect the effect of one or more interventions on human subjects’ biomedical or behavioral status or quality of life. Examples include: positive or negative changes to physiological or biological parameters (e.g., improvement of lung capacity, gene expression); positive or negative changes to psychological or neurodevelopmental parameters (e.g., mood management intervention for smokers; reading comprehension and /or information retention); positive or negative changes to disease processes; positive or negative changes to health-related behaviors; and, positive or negative changes to quality of life.

CS18.0 * Based on the above information, does this study meet the NIH definition of a clinical trial? Yes No

If Yes, click Save and then Click Here For Study Team's CITI Training Records . Please ensure all personnel's training is up to date

[reviewer notes-]

Section 1 - Study Objective, Specific Aims, Background and Significance

1.1 Objective: What is the overall purpose of this research study? (Limit response to 1-2 sentences.)The objective of this study is to assess the efficacy of minimally invasive autologous fat transfer at the amputation sites and the modulation of pain at the respective sites. We hypothesize that autologous fat grafting can provide a minimally invasive therapy facilitated by enabling technology of specialized instrumentation to effectively mitigate pain syndromes at amputation sites, by introducing volume stable

Section: Section 1 - Objective, Aims, Background and Significance

subcutaneous tissue over bony prominences and peripheral nerve trunks, thereby avoiding surgical revisions and preserving limb length. The premise of this study is that we will compare two minimally invasive techniques as an alternative to invasive operations, with the understanding that this therapy does not preclude more invasive procedures in the future. We further hypothesize that enriching the fat graft with autologous adipose stromal cells utilizing the Tissue Genesis Cell Isolation System (CIS), a regenerative medicine approach, will lead to improved retention of the fat graft over time and result in a more favorable outcome.

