
Section: Section 1 - Objective, Aims, Background and Significance

(a similar weight-bearing anatomic region) can be performed safely and effectively with retention rates approximating 75% up to 2 years and beyond (27-29). In an OVID database search of fat grafting articles, over 9000 articles have referenced the use of fat grafts in a wide arena of clinical situations. Specifically to this application over 100 references were relevant to this proposal and provided below.(30-136)Clinically, atrophied fat pads in the weight bearing foot were replaced or supplemented with fat grafts. [Chairman EL. Restoration of the plantar fat pad with autolipotransplantation; J Foot Ankle Surg. 1994 Jul-Aug;33(4):373-9] This procedure was shown to be safe, efficacious and had long term benefits. We propose a clinical trial to assess the efficacy of minimally invasive autologous fat transfer to address pain and poor prosthetic fit at amputation sites. We plan to randomize 15 subjects to the standard fat grafting surgical procedure which involves the immediate transplantation of a subject's own tissue and does not require FDA oversight. Additionally, we will use our knowledge and expertise working with adipose stromal cells to compare a regenerative medicine cell therapy modification of the fat grafting procedure with more traditional fat graft preparations. We plan to randomize 15 subjects to the enriched adipose stromal cells using the Tissue Gensis Cell Isolation System (CIS) IDE # (pending) to process the cells for the modification of the fat grafting procedure. The PI not only has experience with fat grafting in his clinical practice, but also serves as principal investigator in a clinical trial assessing the impact of facial fat grafting for wounded military personnel. The Biomedical Translational Initiative (BTI) (Structural fat Grafting for Craniofacial Trauma, W911QY-09-R-0030) from the Office of the Assistant Secretary of Defense involves the treatment of 20 wounded warriors with facial injuries using minimally invasive fat grafting techniques. This study has established significant infrastructure to evaluate soft tissue reconstruction after facial trauma, and demonstrates the ability of the PI to assemble and manage the team for an interdisciplinary clinical trial. This study, still in progress, has treated 15 subjects out of a targeted enrollment of 20 subjects with no serious adverse events and improved outcomes in all subjects. Another phase of this trial, currently funded through the Armed Forces Institute of Regenerative Medicine (AFIRM) clinical trials program and starting to recruit subjects, assesses the efficacy of a regenerative medicine approach of enriching the fat graft with autologous adipose stromal cells. That same intervention will be trialed in this study, as well. The biggest problem associated with fat grafting is unpredictable rates of fat graft resorption. This is likely related to the ability of the regenerating adipose tissue to rapidly develop a new blood supply. This study will examine if fat grafting with cell enrichment will demonstrate increased fat retention and decreased pain compared to standard fat grafting alone. A modified preparation of the fat graft involves concentrating the endogenous stromal cells in the graft material in an effort to increase graft retention over time. The aspirated fat material used for fat grafting consists of mature adipocytes, a small amount of fibrous tissue, and immature adipose stromal vascular fraction cells (SVFs). These adipose stromal cells are a mixed population of non-lipid laden cells that serve to turn over mature adipocytes and vascular elements. One cell type, "Preadipocytes," or adipose derived stem cells (ASC's), as well as endothelial precursor cells and multilineage

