
recordings. 3.) All participants who are women of child bearing potential will receive a urine pregnancy dip test. If the test result is positive the subject will not continue participation in this research study. 4.) Collection and review of new medications to include prescription and vitamins / supplements, allergies and vital signs (Temp, HR, Resp, BP), weight, body mass index (BMI) calculation, and adverse event reporting. 5.) Serial Computed Tomography Imaging or MRI scan will be performed. A high resolution Computed Tomography (CT) Scan of the amputation stump will be performed at Presbyterian Hospital and will take approximately 60 minutes. This scan will be pre-procedural and will serve as a baseline. All CT scans will be performed on a 64-slice scanner (LightSpeed, GE Healthcare), using slice thickness of 1.25 mm and pitch of 1.375. kVp, mA, and FOV will be optimized to the subject and body part to be imaged. Soft tissue and bone kernels will be employed. These images will be volumetrically reformatted into coronal and sagittal planes for confirmation of findings. Additionally, surface-rendered volumetric reformats will be created emphasizing both bony structures and soft tissues. In the event that a CT scan is contraindicated or declined by a study participant, MRI will be performed using a 1.5 T MRI scanner (Signa HDx, GE Healthcare). The MR imaging protocols will include coronal and axial planes using T1-weighted spin echo sequences as well as coronal, axial, and sagittal planes using T2-weighted fast spin echo with fat suppression and/or short tau inversion recovery (STIR) sequences. Again, FOV, TR/TE time, acquisition time and other parameters will be optimized to the subject and body part to be imaged. Intravenous contrast will not be administered for either CT or MR imaging. Images will be reviewed by radiology. Volume measurements of the implanted material will be made on all post-procedural CTs or MRIs. These volumetric measurements are expected to be precise to within 5% of the actual volume of material. Trends in volume of tissue will be analyzed over time across the multiple CT or MRI scans. Both linear and volumetric measurements will be used to quantify implanted material. Subjects must remove compression sleeves prior to CT scans. 6.) To further evaluate pre-surgical amputation stump pain, the study coordinator will provide a Pain Assessment form to the participant to complete. This form will document the nature/charter of the discomfort limiting function and or interferes with their ability to use a prosthetic device. The subject will be instructed to document the discomfort to include frequency, location, intensity (1 to 10 scale with 10 as most intense), type of pain (physiological or phantom). It will include self interventions related to pain and use of prosthetic devices. 7.) Psychosocial Assessment: One of the aims of the proposed study is to evaluate pre- and post-operative quality of life and symptoms of psychological distress. This aim will also consider psychosocial factors (pre- and post- surgery) that predict psychological well-being and quality of life outcomes following surgery. The aim is important for identification of psychosocial factors that may play a role in and be critical to enhancing quality of life outcomes from amputation stump surgery. Participants will be asked to complete a psychosocial battery that includes: a) self-report measures of satisfaction with physical appearance, anxiety and depressive symptoms, social functioning and social avoidance and distress and; b) questionnaires that assess significant predictors of quality of life

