2.15.3 Will biological specimens be stored without identifiers or linkage codes? *

[reviewer notes-]

Section 2 - Research Design and Methods

2.16 Will research participants be asked to provide information about their family members or acquaintances?

* No

2.16.1 Describe what information about the third party will be obtained from the participant:

2.16.2 If the information about the third party is of a private nature, can the identity of the third party be readily ascertained or associated with this information?

*

Describe the private information that will be collected and recorded about the third party:

[reviewer notes-]

Section 2 - Research Design and Methods

Section: Section 2 - Research Design and Methods

2.17

What are the main outcome variables that will be evaluated in this study?

Primary outcomes: Improvement of pain at the amputation site, improved ability to tolerate a prosthesis, and generation of a stable volume of adipose tissue at the amputation site (as measured by clinical assessment by rehabilitation sciences and prosthetics team, quality of life measures, and high resolution imaging). This will be compared between the standard fat grafting group (n=15) and the adipose cell enriched fat grafting group (n=15). Secondary outcomes: Local and systemic complications resulting from fat graft procedure (infection, fat necrosis, hematoma, seroma); basic assays of adipose cell behavior to elucidate the functional properties of adipose cells used for grafting, with correlation to outcomes.

2.18

Describe the statistical approaches that will be used to analyze the study data.

* Addressed below:

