Pain and Serial computed tomography imaging will be performed and measured as parametric data sets before fat grafting and afterwards at various time points using a paired t-test model. Repeated measures analysis of variance will be used to evaluate change over time in all outcome measures. Using standard conventions of alpha=0.05 and beta=0.8, an enrollment of thirty patients may provide sufficient power to detect a Cohen's effect size of about 0.9 which is anticipated to be adequate for detecting clinically meaningful differences in the volume of soft tissue. A composite functional score will be constructed from the prosthetics and occupational therapy evaluations and compared between study groups. The details of this analysis, including which evaluations will be included in the score and relative weight, can be best determined as the study progresses and initial data sets are acquired. Additionally, each assessment score from the specific tests will also be considered individually for comparison.

[reviewer notes-]

Section 2 - Research Design and Methods

2.19

Will this research be conducted in (a) a foreign country and/or (b) at a site (e.g., Navajo Nation) where the cultural background of the subject population differs substantially from that of Pittsburgh and its surrounding communities?* No

Note that copies of training records, licenses, certificates should be maintained in the study regulatory binder and are subject to audit by the Research Conduct and Compliance Office (RCCO).

Section: Section 2 - Research Design and Methods

In addition, individuals planning to conduct human subject research outside the United States must complete an optional module on the CITI training website: International Studies. Click [here](#) to access the instruction sheet for accessing optional CITI modules.

- 2.19.1 Address the following for each of the foreign/culturally different sites where this research will be conducted:
- Name of site
 - Name of authorized individual (e.g., IRB Chair) from the local IRB or other human subject protections entity that is responsible for the review and approval of the project; upload approval letter with an English translation, if applicable
 - Name and qualifications of the site collaborator responsible for the conduct of the research (e.g., site PI)
 - The anticipated number of subjects that will be enrolled at that site
 - If Federally funded, provide the Federalwide Assurance number (FWA) assigned to the site *

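### Section 2.17 promises a 15 vs 15 comparison of pain and graft volume, but the tests that 2.18 names for them state no arm term, readout visit or limb stratum

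*Combined protocol and SAP*

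**What the plan says.** Section 2.17 lists three primary outcomes: pain, tolerance of a prosthesis, and a stable volume of adipose tissue. It then says: "This will be compared between the standard fat grafting group (n=15) and the adipose cell enriched fat grafting group (n=15". Section 1.1 hypothesises that enrichment "will lead to improved retention of the fat graft over time and result in a more favorable outcome". Section 1.3 puts the randomised question directly: "This study will examine if fat grafting with cell enrichment will demonstrate increased fat retention and decreased pain compared to standard fat grafting alone".

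Section 2.18 names two methods that apply to pain and imaging:

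- a paired t-test, with the data "measured as parametric data sets before fat grafting and afterwards at various time points using a paired t-test model";
- an ANOVA: "Repeated measures analysis of variance will be used to evaluate change over time in all outcome measures".

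Only the composite functional score is expressly to be compared between study groups. The specific tests behind it follow: "each assessment score from the specific tests will also be considered individually for comparison". No test is named for either. The power sentence says that "an enrollment of thirty patients may provide sufficient power to detect a Cohen's effect size of about 0.9". It refers to soft-tissue volume, not pain, and gives no test or sidedness.

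Randomisation is in blocks of six (3 and 3) within upper or lower limb (sections 2.5.1 and 3.12). Both sections say this will permit the treatments to be examined within each block, but they name no method. Limb pain is assessed at all six numbered post-operative visits, and scans are done at months 6, 12 and 24 (section 2.7). On imaging, section 2.6 says: "Volume measurements of the implanted material will be made on all post-procedural CTs or MRIs".

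**The concern.** The trial randomises in order to learn whether enrichment adds to standard grafting. The methods named for pain and volume ask whether patients differ after grafting from before, and whether outcomes change over time. A positive answer to either is compatible with no difference between the arms, so the plan promises one comparison and writes down tests for another.

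Three choices are left open: whether and how arm enters the model, which visit or contrast decides, and whether the limb stratum used in randomisation is used in the analysis. In a non-blinded trial (section 2.3) with six pain assessments and three scans, these should be settled before any outcome is seen. A pilot can accept low power, but it still needs a stated test for the comparison it promises.

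**Working it through.** **Inputs from the documents.** 15 per arm; alpha 0.05; effect size about 0.9 (section 2.18). I read the stated beta of 0.8 as power 0.8. Read literally as power 0.2, the detectable d would be 0.42 two-sided or 0.30 one-sided, which does not match 0.9. Blocks are 3 vs 3 (sections 2.5.1, 3.12). There are six pain visits and three post-graft scans (section 2.7).

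**Assumed, because the documents give no figure.** Within-patient change, baseline-to-follow-up correlation rho, and between-visit correlation r.

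**1. Which test gives about 0.9?** Noncentral t throughout. For the paired test the noncentrality is d√n on n−1 df. For two samples it is d√(n/2) on 2n−2 df; at d=0.9 and n=15 that is 0.9 × √7.5 = 2.46 on 28 df. Baseline adjustment multiplies the detectable d by √(1−rho²).

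| Test | Detectable d at 80% power |
|---|---|
| Paired, two-sided, n=30 | 0.53 |
| Paired, two-sided, n=15 | 0.78 |
| 15 vs 15, two-sided, unadjusted | 1.06 (power at 0.9: 66%) |
| 15 vs 15, one-sided, unadjusted | 0.93 (power at 0.9: 78%) |
| 15 vs 15, two-sided, baseline-adjusted, rho 0.5 | 1.06 × √0.75 = 0.92 |

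The plan's figure is reproduced by a one-sided two-sample test. A two-sided adjusted test also reaches it at rho 0.5. So does a two-sided comparison of three-scan means: the factor √((1+2r)/3) gives 0.87 at r=0.5 and 0.95 at r=0.7. All of these are between-arm tests, and 2.18 names none of them.

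**2. What the paired test shows when enrichment adds nothing.** With n=30 and an assumed within-patient d of 0.3, 0.5 or 0.7, the probability of significance is 36%, 75% or 96%. A simulation of 8,000 trials with rho 0.5 and no arm difference gave the same figures. In the same trials the arm term of a baseline-adjusted model was significant in about 5%. The two results are not rival error rates. The first is power for a true grafting change, and the second is the type I error for enrichment. They show that the tests answer different questions.

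**3. Comparison within a block.** For 3 vs 3 at d=0.9, two-sided, power is 14%. Examining treatments block by block does not replace a stratum-adjusted comparison of all 30.

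**4. Cost of an open readout.** Suppose an unadjusted 15 vs 15 t-test were run at each visit and any p<0.05 kept, with no true difference (40,000 simulated trials):

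| Assumed r | Six pain visits | Three scans |
|---|---|---|
| 0.3 | 24% | 14% |
| 0.5 | 21% | 13% |
| 0.7 | 17% | 11% |

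**5. Gain from adjustment.** Two-sided power at d=0.9 is 66% unadjusted. By formula, adjustment for baseline gives 70%, 78% and 91% at rho 0.3, 0.5 and 0.7. Simulations that fit baseline and an assumed 24/6 split of lower and upper limbs give 68%, 77% and 90%.

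**6. Volume.** Implanted material has no pre-graft value. The first post-graft scan is at month 6. The stated exposure agrees: 5.2 rem ÷ 1.3 rem per scan = 4 scans, one before grafting and three after (section 5.1). Percent retention of the graft therefore needs the injected volume. Section 2.6 expressly records the cell dose and does not expressly say that injected volume is recorded.

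**The case against.** The first stated objective (section 1.1) is whether fat grafting itself relieves pain, and a before/after test is a natural, if uncontrolled, way to address it. Section 2.18 never says the paired test will support the enrichment claim. That stands. A reader might take 36%, 75% and 96% as false-positive rates for enrichment, but the documents assign the paired test no such role.

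Repeated-measures ANOVA can carry a group factor, and 2.17, directly above, promises the comparison. A reader might infer that the plan excludes an arm comparison of pain and volume. It does not: the arm term is unstated, and sections 2.5.1 and 3.12 do state an intent to examine treatments within blocks. What remains is that no method is given.

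The visit-choice rates belong to a procedure that 2.18 does not prescribe, and an ANOVA over visits would pool them. That is right. The rates show what the open wording fails to exclude.

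The power figure is not shown to be wrong, since several between-arm tests reach about 0.9. The fault is only that test and sidedness are missing.

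On volume, a reader might infer that retention can only be judged against injected volume. Sections 2.6 and 2.17 also support stability from scan to scan, which needs no injected volume. Nor do the documents show that a before/after volume test is bound to be positive: the 5% precision in section 2.6 is for implanted material, and no error is given for limb volume. Injected volume may well be recorded, since the cell target is per ml of graft, but the intraoperative source document is not among the texts reviewed.

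**Conclusion.** The concern holds as a mismatch between the promised comparison and the named tests. For pain and adipose volume, 2.18 states two analyses of change and no arm term, readout or stratum factor. As written, neither is specified to answer the enrichment question.

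The effect size of about 0.9 points to a between-arm test that was never written down. That match rests on reading beta as power and, for the adjusted test, on an assumed correlation of 0.5. The 11% to 24% visit-choice rates hold only if each visit is tested separately and any significant result is kept. They also assume equal correlation between visits. None of this shows that the trial will be analysed wrongly. It shows that the plan leaves the main randomised analysis to be settled later. It should be fixed, and the change is small.

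**What to change.** Change section 2.18 as follows.

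- **Pain:** make the enrichment analysis a between-arm ANCOVA, or a mixed model with arm-by-visit, in all randomised patients. Adjust for baseline pain and the upper/lower limb stratum, and name one readout visit or contrast in advance.
- **Implanted graft volume:** use a between-arm comparison adjusted for the stratum, with one named measure and readout. If the measure is percent retention, or uses injected volume as a covariate, confirm that injected volume is recorded for every patient and report it by arm. The surgeon sets it in a non-blinded trial, so it should be read beside the result.
- **Paired tests:** keep them, labelled as uncontrolled evidence on grafting and not on enrichment.
- **Composite and individual scores:** name the between-arm test.
- **Power sentence:** restate it for the chosen test, with its sidedness and any assumed correlation.

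The cost is plan wording, one or two degrees of freedom, and possibly one more field in the intraoperative source document. The power gain is small if the baseline correlation is low: from 66% to about 68–70% at 0.3.

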
Section: Section 1 - Objective, Aims, Background and Significance

program, led by [name] (Co-Director of the Adipose Stem Cell Center) in collaboration with [name], director of the clinical laboratories for cell processing. We are currently starting a fully funded project with the Armed Forces of Regenerative Medicine (AFIRM). We are utilizing our extraction techniques to perform SVF enriched fat grafting for facial trauma reconstruction and this has received IRB approval at our institution. This process is regulated under human cells, tissues and cellular and tissue-based products (HCT/P) guidelines under section 361 of the CFR (21CFR1271.10). HCT/P therapies are exempt from the requirement for the submission of an Investigational New Drug (IND) application. For this project proposal, we have expanded the team to encompass expertise in reconstructive fat grafting, lower extremity reconstruction, physical medicine and rehabilitation, prosthetic design, nutritional support, and evaluation of psychosocial outcomes. Given the initial success with autologous fat grafting for facial reconstruction after trauma (analysis ongoing), even without enrichment of the graft with adipose stromal cells, we believe this therapy can be effectively applied for the treatment of limb pain. This procedure can be performed on an outpatient basis with no significant incisions on the limb, only small port sites measuring less than 5 mm. It is noted that this is a completely new, experimental application of a conventional treatment.

1.4

Significance: Why is it important that this research be conducted? What gaps in existing information or knowledge is this research intended to fill? This study will significantly impact military trauma care by validating a minimally invasive cell based technique for alleviating pain at amputation sites and improving function with a prosthesis. Importantly, the goal will be reached without invasive surgery, increased risk, and a prolonged recovery. Given the high amputation rate in the current conflicts, this work is highly relevant to the care of the wounded warrior. A major goal of this study will be to transfer the techniques and knowledge gained to physicians throughout the Department of Defense healthcare system, as well as the general US healthcare team who treats amputees from non-military trauma and illness.

Section: Section 2 - Research Design and Methods

[reviewer notes-]

Section 2 - Research and Design Methods

2.1

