needed to treat scarring. Seroma: Although unlikely, a collection of fluid may appear at the site where the fat was removed. This is usually treated by draining the fluid with a needle. Infection: risk of infection may occur secondary to the multiple small incisions from the liposuction procedure. Infection is unusual after this procedure. Should infection occur, additional treatment including antibiotics or surgery may be necessary. Long term effect: subsequent changes in the shape or appearance of the area where the fat was removed or placed may occur as a result of aging, weight loss or gain, or other circumstances not related to the Fat grafting procedure. Chronic pain may occur rarely after fat removal or grafting. Unsatisfactory result: There is a possibility of unsatisfactory result from the procedure resulting in unacceptable visible deformities, loss of function, wound disruption, healing problems, and loss of sensation. Allergic reaction: In rare cases local allergies to tape, suture material, or topical preparations have been reported. Systemic reactions, which are more serious, may result from drugs used during the procedure. This is an extremely rare occurrence. Damage to deeper structures: Deeper structures such as nerves, blood vessels and muscles may be damaged during the course of this procedure. The injury to deeper structures may be temporary or permanent. Serious complications may include blood clots, partial collapse of lungs, pulmonary embolism, fat embolism, stroke, infection. Serious complications after fat grafting are rare such as blindness loss of vision, and/or death.

Other Risks: Scarring: All invasive procedures produce scars, some more visible than others. Although good wound healing after a procedure is expected, abnormal scars may occur both within the skin and within the deeper tissues. Scars may be unattractive and of different color than the surrounding skin. There is the possibility of visible marks from sutures used to close the wound. Scars may also limit motion and function. Additional treatment including surgery may be needed to treat scarring. Long term effect: subsequent changes in the shape or appearance of the area where the fat was removed or placed may occur as a result of aging, weight loss or gain, or other circumstances not related to the Fat grafting

| | |
|------|---|

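### Section 2.18 names no valid method for complications, and neither of its tests can show that graft volume is stable

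*Combined protocol and SAP*

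**What the plan says.** Section 2.17 gives three primary outcomes, one of which is "generation of a stable volume of adipose tissue at the amputation site". It then lists "Secondary outcomes: Local and systemic complications resulting from fat graft procedure (infection, fat necrosis, hematoma, seroma", together with the adipose cell assays. The primary outcomes are to be compared between two arms of 15.

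Section 2.18 gives the methods. Pain and CT imaging are measured before grafting and "afterwards at various time points using a paired t-test model". Then: "Repeated measures analysis of variance will be used to evaluate change over time in all outcome measures". A composite functional score and the individual assessment scores are compared between groups. No method for proportions or event counts is named, and stable has no numerical definition.

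Other relevant text:
- Section 2.3 describes the trial as a non-blinded pilot.
- Section 2.6 says the volume of the implanted material is measured on every post-procedural scan and that trends across scans will be analysed.
- Section 2.7 places those scans at months 6, 12 and 24 and collects adverse events at every post-operative visit.
- Section 5.7 commits to capturing all complication data.

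**The concern.** **Complications.** Analysis of variance of change over time assumes a roughly continuous response measured repeatedly. Infection, hematoma and seroma are rare yes/no events that are absent at baseline by definition. Means and residual variances of such data with 15 patients per arm give neither a usable estimate nor a trustworthy p-value. The restriction to events resulting from the procedure adds a judgement made by people who know the arm, so attribution can differ between arms. This matters because the protocol itself foresees hazards specific to the enriched product: section 2.6 staggers the first six device-arm subjects to watch for anaphylaxis and contamination, and section 5.1 notes up to 30 minutes of extra operating time.

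**Stable volume.** Stability is a claim that change is small. A test of no change can reject that hypothesis but cannot establish it, and with few patients a real loss will often be non-significant. The before/after test answers a different question: whether any graft is left.

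**Working it through.** **The plan's own figure.** The only sizing statement is "Using standard conventions of alpha=0.05 and beta=0.8" (0.8 is evidently the power), with "an enrollment of thirty patients may provide sufficient power" for a Cohen's effect size of about 0.9 in soft-tissue volume. With 15 per arm the noncentrality is 0.9 × √(15/2) = 2.46. The t-test power is 0.78 one-sided and 0.66 two-sided, and the effect detectable at 80% power is 0.93 or 1.06. So the figure is close if the test is one-sided; sidedness is not stated. It concerns volume only. Nothing in the plan is sized for complications or for showing stability.

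**Complications, 15 per arm (sections 2.17 and 3.11).** The documents give no complication rates, so the rates used for power are assumptions.
- Upper limit after 0/15 (Clopper-Pearson): 1 − 0.025^(1/15) = 21.8% two-sided; 1 − 0.05^(1/15) = 18.1% one-sided.
- Interval for the difference (Newcombe, used here as an approximation to an exact interval): 0/15 v 0/15 gives about ±20 points; 1/15 v 1/15 gives about ±24 points.
- Fisher's exact test against 0/15: 4/15 gives p = 0.0996; 5/15 gives p = 0.042. At least five events against none are needed.
- Fisher power by enumeration: 5% v 20%, 8%; 10% v 30%, 15%; 10% v 40%, 33%.

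**Failing to find a volume change.** Take a true loss of 10 points between months 6 and 24, in percentage points of injected volume. The SD of the change is not given, so 20, 30 and 40 points are assumed. Paired t-test, two-sided 0.05, noncentrality (10/SD) × √n:

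| SD of change | Non-significant, n=30 | Non-significant, n=15 |
|---|---|---|
| 20 | 25% | 56% |
| 30 | 58% | 77% |
| 40 | 74% | 85% |

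**The before/after test.** The implanted volume is zero before grafting, so the paired difference is simply what survives. Suppose 70% of the graft is lost: mean retained 30 points, SD 30 (assumed), n=30. Then t is about 30/(30/√30) = 5.48 and power is 0.9996. If total soft tissue at the site is compared instead, the difference still mainly reflects surviving graft. Either way, a significant result is compatible with losing most of it.

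**Why a month-24/month-6 ratio needs company.** If 100 units are injected, 30 remain at month 6 and 30 remain at month 24, the ratio is 30/30 = 1.0 although 70% was lost. The ratio speaks only to loss after month 6.

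**The case against.** **Omission rather than prescription.** The sentence in 2.18 is about change over time, and the assays, also secondary, are to be correlated with outcomes. So the reference to all outcome measures may be loose drafting that was never meant to cover events. That is a fair reading of intent. It leaves complications with no method at all, and the remedy is the same.

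**Safety is already overseen.** Adverse events are collected at each visit, complication data are captured in full (5.7), and an independent board and a research monitor review events (5.13). This stands, and it means no new data are needed. None of it supplies a comparison by arm.

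**This is a pilot.** Descriptive safety reporting is normal, and no method gives 15 per arm much precision. That is correct, and it is why the fix asks for counts and intervals rather than a better test.

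**Stronger readings the documents do not support.**
- A reader might infer that the trial plans to conclude that enrichment adds no risk. Section 1.4 says "Importantly, the goal will be reached without invasive surgery, increased risk, and a prolonged recovery", but in context this contrasts fat grafting with invasive revision surgery, so an interval for the difference between arms could not replace it. Section 1.3 does say concentrating the cells is not expected to add risk, as background. No safety hypothesis or margin is set.
- A reader might infer that analysis of variance is wrong for volume. It is a reasonable model for a continuous, repeatedly scanned measure; what is missing is an estimate and a criterion.
- A reader might infer that a non-significant change will be read as stable. No section says so, and the hypothesis in 1.1 is superior retention with enrichment. The point is that the plan offers nothing else by which to judge stability.
- A reader might infer that weight must be adjusted for, since 5.1 says changes in shape or appearance "may occur as a result of aging, weight loss or gain, or other circumstances not related to the Fat grafting" procedure. That is risk-disclosure text, weight is not listed at the day 3-6 visit, and adjustment for a post-randomisation variable is optional.

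**Conclusion.** The point holds in two parts. First, 2.18 as written assigns an unsuitable method to complications and names no other, and the attribution filter is open to bias in a non-blinded trial. Second, stable volume is a primary outcome with no criterion, and neither the test of no change nor the before/after test can establish it.

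The limits that follow from n alone are firm: 0/15 leaves up to 21.8%, and five events against none are needed for significance. The Fisher power figures rest on assumed event rates, and the 25% to 74% and 0.9996 figures on assumed SDs. All are before dropout. Severity: should-fix. The defect is in wording and reporting, in a self-described pilot, and can be settled before analysis.

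**What to change.** In section 2.18:

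1. **Complications.** Exclude them from the analysis of variance. Report, by assigned arm and regardless of attribution, the number of patients with at least one local or systemic complication through month 24, with exact 95% confidence intervals for each arm and for the difference. State that with 15 per arm even 0/15 leaves an upper limit of about 22%, so absence of a difference will not be reported as evidence that enrichment adds no risk.
2. **Volume.** Report graft volume at months 6, 12 and 24 by arm with 95% confidence intervals, and the month-24/month-6 ratio with its 95% interval. Call volume stable only if the lower limit of the ratio exceeds a margin fixed before scans are read. Always show month-6 retention beside it, and say how patients with almost no graft at month 6 are handled, since the ratio is uninformative for them. Repeated-measures analysis of variance can stay for the comparison of volume over time. Adjustment for body-weight change may be added as an optional sensitivity analysis.

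Section 1.4 needs no change on this account. The cost is a paragraph of plan text and a few tables, with no new data. The downside is that the safety and stability statements become weaker, and the investigators must commit to a margin that the documents do not supply.
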